**1) Protocol Title**

Preventing Cognitive Decline in HIV-infected Latinos through a Culturally Tailored Health Promotion Intervention (HOLA)

**2) IRB Review History\***

This protocol has not been submitted for review by an external IRB.

**3) Objectives\***

The project will conduct a pilot single-arm trial with Latinos living with HIV (LWH) to assess feasibility, acceptability, and preliminary effects on cognition for a fully powered randomized trial (R01).

**Specific Aim 1:** To determine feasibility and acceptability of HOLA, adapted to incorporate a cognition focus, aimed at improving cognitive functioning among older Latinos LWH and incorporating activity tracking (Fitbit);

**Specific Aim 2:** To explore whether HOLA will produce changes in cognitive functioning between baseline and post-test (16 weeks);

**Specific Aim 3:** To explore whether HOLA will produce changes in activity, psychosocial functioning (depression, anxiety, social support) or biomarkers of cognition (myokines/cytokines [IL-15], adipokines [irisin and adiponectin], neurotrophic factors [BDNF, IGF-1 VEGF]) between baseline and post-test; and APOE e4 carrier status (a genetic risk for dementia) baseline only.

**Specific Aim 4:** To explore whether changes in activity, psychosocial functioning or cognitive biomarkers correlate with changes in cognition, while accounting for genetic risk for dementia (APOE e4 carrier status).

**4) Background\***

Advancements in the treatment of HIV over the past two decades have greatly improved the longevity and health of people living with HIV (LWH). However, neurocognitive impairment among people LWH continues to be common and impactful and is observed in up to half of persons LWH. Non-pathological cognitive impairments are found in numerous aging studies and HIV studies.

Although HIV-related dementia is not as prevalent with the advent of Antiretroviral Therapy (ART), adults with HIV remain susceptible to both cortical and subcortical insults that produce cognitive impairments. In 1,555 adults with HIV from across the United States, Heaton et al. found 52% experienced measurable cognitive impairments with 33%, 12%, and 5% experiencing Asymptomatic Neurocognitive Impairment, Mild Neurocognitive Disorder, and Mixed Neurocognitive Disorder, respectively. Such cognitive impairments may be attributable to factors such as: the death of glial cells caused by HIV; elevated cortisol levels and inflammation caused by HIV; age- and HIV-associated comorbidities; and ART-induced metabolic complications such as hypercholesterolemia and insulin resistance. For example, Justice et al. found a

IRB Study Number: 20201202  
Version 4.02, Date: 11/10/2021

high prevalence of cognitive impairments (e.g., speed of processing, memory) in middle-aged and older veterans with HIV. Both viral burden and older age are significant predictors of such cognitive impairment. Studies have also found cognitive declines and changes in brain functioning in adults with HIV as early as 1 year following infection. These declines occur across cognitive domains but are most often observed in speed of processing. Latinos LWH may be uniquely at risk for deleterious neuropathological and neurocognitive sequelae within the context of aging. Ethnic differences on cognitive impairments were evident across the domains of memory, executive functioning, and speed of information processing. Most of the neurocognitive domains in which there were significant ethnic differences are among the most commonly impacted by HIV in the combination ART era and are linked with problems in everyday functioning in people LWH. Furthermore, depression among older Latinos LWH has been reported at five times the level in the general population and is fueled by stigma and resultant loneliness due to rejection and withdrawal. Depression has been identified as an independent risk factor for cognitive impairment among older adults LWH. Thus, there is a growing population that is particularly vulnerable to dementia due to the co-occurrence of HIV, depression, and aging-related cognitive impairments.

## 5) **Inclusion and Exclusion Criteria\***

### *Inclusion Criteria:*

The following conditions must be met for study eligibility:

- are Latino (self-identified);
- are age 50+;
- are HIV infected but are virologically suppressed (viral load <200 copies/mL);
- volunteer informed consent;

### *Exclusion Criteria:*

Individuals meeting any of the following criteria will not be eligible to participate in the study:

- have diagnosis of any neurodegenerative disorder or dementia (Parkinson's disease, Alzheimer's disease, vascular, frontotemporal dementia, etc.) or significant cognitive impairment as indicated by a Telephone Interview for Cognitive Status (TICS) score less than or equal to 30;
- have other conditions that could impact cognitive functioning or testing (e.g., legally blind or deaf), currently undergoing radiation or chemotherapy, a history of brain trauma with a loss of consciousness greater than 30 minutes.
- have contraindications to physical activity outlined in the American College of Sports Medicine standards or severe medical illness that

IRB Study Number: 20201202  
Version 4.02, Date: 11/10/2021

precludes them from safely participating in a health promotion intervention.

- are unable to complete 10-meter walk test.
- have plans to move outside of the Miami metropolitan area within the next 6 months or are not living in stable housing (e.g. group home).

This study will include both men and women; no decision to exclude any person from this study will be based on gender. We do not expect there to be any difference in the number of women and men. This study will specifically target Latinos. Individuals from other ethnic backgrounds are excluded as the study intervention is specifically tailored to address and target the specific needs and preferences of older Latinos at increased risk for cognitive impairment.

**6) Number of Subjects\***

30 older Latinos age 50+ will be enrolled. Consistent with recommendations from biostatistical workgroups funded by NIH, this pilot study is not powered to test hypotheses. The proposed project builds upon recruitment and intervention infrastructure that is being used in other HOLA studies. Participants will not be replaced if withdrawn or lost to follow-up.

**7) Study-Wide Recruitment Methods\***

We will collaborate with another study, the Clinic Registry Project (IRB#20160911), which serves as a database, to contact eligible participants. They will provide us with contact information for participants in their study who have consented to be contacted by other studies. When contacting participants, the community health worker (CHW) will follow the phone script.

**8) Procedures Involved\***

Participants will be assessed at two time points (baseline and post intervention at 16 weeks) on measures of neurocognitive and psychosocial functioning. Blood will be collected to determine APOE (baseline only) and biomarkers of cognition (baseline and 16-weeks).

All participants will read and sign an informed consent. They will initially be provided with a verbal summary of the study and for those who appear to have problems reading the consent form it will be read aloud. Participant payments will be graduated. Participants will receive \$25 on the first visit and \$35 on the second visit (total of honoraria = \$60). They will also be given the Fitbit tracking device to keep.

IRB Study Number: 20201202  
Version 4.02, Date: 11/10/2021

Prior to starting the baseline assessments, blood draws will take place at the CTRS. Approximately 20mL (2 tablespoons) of blood will be collected by a trained phlebotomist. Study staff will obtain biomarkers of cognition (myokines/cytokines [IL-15], adipokines [irisin and adiponectin], neurotrophic factors [BDNF, IGF-1 VEGF]) as well as apolipoprotein E (APOE) status, a genetic marker of dementia risk (baseline only).

Trained and certified bilingual research assistants (RAs) who have at least a bachelor's degree will conduct all assessments in private offices at the Soffer Clinical Research Building (CRB) or another location convenient to the participant where privacy can be protected. The neurocognitive testing will be conducted under the supervision of a neuropsychologist. Approximate administration time of the assessment will be 60 minutes.

IRB Study Number: 20201202  
Version 4.02, Date: 11/10/2021

### Assessment Measures

Dementia Screen: The Telephone Interview for Cognitive Status (TICS) will be used to screen for dementia. A score of 30 or below indicates cognitive impairment.

Walking Ability: The 10-meter walk test will be used to evaluate walking ability, which has been used as a screening instrument to measure functional mobility and gait speed in physical activity interventions with older adults.

Demographics: The Center for Latino Health Research Opportunities (CLaRO) Demographics Form will be used to collect demographic information (e.g., gender, education, income, preferred language, country of origin, time in the US, etc.) and will include a list of all diagnosed medical conditions and medications.

Acculturation: The 24-item Bidimensional Acculturation Scale (BAS) will be used to measure acculturation.

Depression Severity: The 9-item Patient Health Questionnaire (PHQ-9) will be used to measure depression severity.

Anxiety Severity: The 7-item Generalized Anxiety Disorder (GAD-7) scale will be used to measure anxiety severity.

Social Support: Perceived social support will be measured using the 12-item Multidimensional Scale of Perceived Social Support (MSPSS).

Physical Activity: The 16-item Global Physical Activity Questionnaire (GPAQ) will be used to measure physical activity.

Processing Speed: Trails Making Test A will be used to measure processing speed.

Attention/Working Memory: The WAIS-IV Digit Span will be used.

Learning: Hopkins Verbal Learning Test-Revised (HVLT-R)

Memory: HVLT-R Delay

Verbal Fluency: Animal Fluency and Controlled Oral Word Association Test (COWAT)

Executive Function: Trails Making Test B

IRB Study Number: 20201202  
Version 4.02, Date: 11/10/2021

Motor: Grooved Pegboard (dominant and non-dominant)

Biomarkers of cognition: Myokines/cytokines (IL-15), adipokines (irisin and adiponectin), and neurotrophic factors (BDNF, IGF-1 VEGF)

Genetic risk factor for dementia (baseline only): Apolipoprotein E (ApoE)

#### Intervention Description: Content and Structure of HOLA

HOLA is a multi-component, health promotion intervention for older Latinos.

The first component consists of two manualized social and physical activation sessions. Prior to beginning the group walk phase, each participant will meet individually with a CHW for a 30 minute physical and social activation session to (a) educate potential participants about the goals of the intervention; (b) provide information surrounding cognitive functioning, age-related memory loss vs. dementia, difference between dementia and Alzheimer's disease, how their comorbidities impacted cognition, and ways they can prevent cognitive decline and the; (c) motivate participants to engage in physical activity; (d) increase participants' social activities (e) identify potential obstacles that may interfere with meeting the demands of the intervention; and (f) brainstorm ways to overcome these obstacles. Participants will again meet individually with the CHW for 30 minutes after week 8 to discuss progress of physical and social activity goals. In addition, during this session, the CHW goes over the ground rules for the intervention and reminds each participant that it is important that we create a comfortable environment where every member of the group is free to share thoughts, feelings and experiences. In order to do this, we ask that each participant not discuss other group members' personal information with anyone outside of the walking group. This helps us to know that anything shared will not go beyond the walking group. These meetings are held in the participants' homes.

The second component is a group walk, led by a CHW for 45 minutes, 3 times a week, for 16 weeks. The group walk protocol uses the concept of interval training. The program starts slowly and gradually increases in workload by manipulating three factors: (a) intensity: governed by speed; (b) volume: duration and/or distance; and (c) work/recovery cycle: how long work phase lasts compared to the recovery phase. Walks will be conducted with a group of 6 participants. Each walk will begin with 10 minutes of stretching and warm up. Then, participants will walk for 30 minutes. The walk will conclude with 5 minutes of cool down. The groups will include bilingual and monolingual Spanish speaking participants.

The third component consists of scheduling pleasant events. During the cool down phase of each walking session, the CHW will ask each participant to identify a pleasant event that they intend to do with another person before the next

IRB Study Number: 20201202  
Version 4.02, Date: 11/10/2021

meeting. Individuals may choose to do this activity with another member of the group, with family, or with friends outside the group. Subsequent sessions will start with participants reporting on how effectively they implemented their pleasant event plan while the CHW and the group provide positive reinforcement and feedback. This component provides a means to generalize the intervention into the participants' everyday lives and relationships. Participants will walk at a centrally located public park, which is owned and operated by the Miami-Dade County Parks and Recreation Department.

A fidelity measure has been developed to assess the consistency with which different CHWs deliver the HOLA intervention. This is an anchored rating scale characterizing core components of HOLA. Mental health specialists will be supervised and give one-on-one feedback to the CHWs. If there is drift, adjustments will be made to make sure that what is being delivered is fully consistent with the intervention as designed. In addition, [name] will attend five walking sessions for every group to supervise and provide corrective feedback as needed. There will also be a detailed manual of operations.

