Breach of Confidentiality Risk: The study also involves talking in a group setting during the walking sessions. Participants will be asked not to discuss other group members' personal information with anyone outside of the walking group. They will be asked to not share the names of fellow group members with anyone. Participants will also be reminded that they do not have to share information that they are not comfortable discussing. Although the CHW will remind all participants to keep the walk discussions private, this cannot be guaranteed.

Our staff is CITI certified and trained in the maintenance of confidentiality. The information provided by study participants will be held as personal and confidential to the extent permitted by law. In addition to the safeguards included as part of the recruitment and screening process by assigning a patient a study ID to de-identify participants, all study participants will be given the contact information for the Principal Investigators to answer any questions that may arise. Participants will be informed that they may end their participation at any time without affecting access to any services they are receiving. All study procedures will be conducted according to good clinical practice and all other relevant regulatory guidelines.

All electronic data will be stripped of identifiers and stored in password-protected files on servers at the Department of Psychiatry and Behavioral Sciences. These data are password secured for minimal access to authorized personnel associated with the study. For each data file, a code number will be assigned, and the master list, linking code numbers with names, will be stored separately. At the conclusion of the project, the record linking the assigned research number and participant identity will be destroyed. Data will be entered into password secured databases by staff authorized by the principal investigator to do this, and they will abide by confidentiality regulations of the HSRO. No subject will be identified by any published report.

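### Read literally, the protocol puts the individual review of ground rules and confidentiality after week 8, when at least 24 of 48 planned group walks are over, and no section places the request before the first walk

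*Combined protocol and SAP*

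**What the plan says.** The Intervention Description in section 8 opens the first component this way: "The first component consists of two manualized social and physical activation sessions".

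- **First session.** "Prior to beginning the group walk phase, each participant will meet individually with a CHW for a 30 minute physical and social activation session". Its content is itemised (a) to (f): goals of the intervention, education about cognition, motivation for physical activity, social activity, obstacles, and ways round them.
- **Second session.** "Participants will again meet individually with the CHW for 30 minutes after week 8 to discuss progress of physical and social activity goals".
- **Ground rules.** The very next sentence begins: "In addition, during this session, the CHW goes over the ground rules for the intervention". The same passage of text goes on to the need for a comfortable environment, and then to the request itself: "we ask that each participant not discuss other group members' personal information with anyone outside of the walking group".
- **Walks.** "The second component is a group walk, led by a CHW for 45 minutes, 3 times a week, for 16 weeks". "Walks will be conducted with a group of 6 participants".

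Section 13 (Potential Risks, Breach of Confidentiality Risk) names talking in the walking group as a risk. It repeats the request about personal information and adds: "They will be asked to not share the names of fellow group members with anyone". It also says that members will be told they need not share what they are uncomfortable discussing, and that the CHW will remind them to keep walk discussions private. It concedes that privacy cannot be guaranteed. It does not say when any of this happens.

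**The concern.** A request for confidentiality protects best if it is made before people start sharing. In this trial sharing starts early. From the first walk, each member names a pleasant event to do with another person, who may be a fellow member, a relative or a friend, and reports on it to the group at the next session. The walks take place in a public park.

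The information at stake is sensitive. Section 5 requires every participant to be HIV infected, and the walking groups are made up of participants. Identifying a fellow member to someone who knows how the group is composed would therefore reveal that person's HIV status. Section 4 links stigma to depression in this population.

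The wording also matters for delivery. Section 8 describes the sessions as manualized and provides a fidelity rating, with drift corrected back to the intervention as designed. The design text should therefore be clear about when the rules are covered.

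**Working it through.** The protocol states no figure for this point, so there is nothing to reproduce. The check has two parts.

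**1. Which session carries the ground rules?**

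| Place | Content | Timing given |
|---|---|---|
| Section 8, first individual session | Items (a) to (f); no ground rules, no confidentiality request | Before the walks |
| Section 8, second individual session | Progress on activity goals | After week 8 |
| Section 8, next sentence | Ground rules, then the request about members' information | The session just referred to, in the singular |
| Section 13, Breach of Confidentiality Risk | Same request, plus names, plus CHW reminders | None |

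The singular reference follows directly on the sentence about the meeting after week 8, and it is introduced as an addition to that meeting's purpose. The literal reading is therefore the second session. No visible section says that the request is made before the first walk.

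**2. How much group contact comes before that session?** The inputs, all from section 8, are 3 walks a week, 16 weeks, 45 minutes a walk, and a second session after week 8.

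- Planned walks: 3 × 16 = 48.
- Walks by the end of week 8: 3 × 8 = 24.
- Share: 24 / 48 = 50%.
- Group contact time: 24 × 45 minutes = 1,080 minutes = 18 hours. The stated walk length is consistent with its parts: 10 + 30 + 5 = 45 minutes.

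The protocol gives no latest date for the second session, so 50% is the minimum on the planned schedule. Two assumed later dates show the range:

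- End of week 9: 27 / 48 = 56%.
- End of week 10: 30 / 48 = 63%.

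**The case against.** The strongest reply is that this is unclear drafting and not a decision to delay the rules. The paragraph describes both individual sessions together, and the ground-rules sentence may be a misplaced description of the first. The CHW is also said to remind participants, which could suit a refresher of something already said. This stands in part: a drafting slip cannot be excluded. However, the reminding is grammatically about the comfortable environment, not about the confidentiality request, and no earlier instruction is described.

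The second reply is that section 13 covers the matter. It makes the same requests without tying them to week 8, and it speaks of the walking sessions generally. This also stands in part. Section 13 may well describe requests made throughout the walks. Because it is undated, it cannot show that they precede the first walk.

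A reader might infer that participants hear nothing about confidentiality for eight weeks. The documents do not support that. The intervention manual and the manual of operations are not included, the consent pages were removed before review, and section 13 leaves room for an earlier request.

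A reader might also infer that naming a member always discloses HIV status. It does so only where the listener knows that the group consists of people with HIV; section 8 describes HOLA more broadly, as health promotion for older Latinos. Nor do the documents give any rate of breaches, or of dropout caused by them, so no effect on the retention or attendance criteria can be claimed.

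**Conclusion.** The point holds as one of stated timing. On the literal text of section 8, the individual review of ground rules and confidentiality falls after at least half of the planned walks, and the itemised pre-walk session omits it. Section 13 relies on the same kind of request as a safeguard but does not date it.

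The conclusion rests on two assumptions: that the singular reference means the session just described, and that walks run to schedule from week 1. That the groups contain only people with HIV is inferred from the inclusion criteria and the make-up of the groups; no section uses that description. The 50% measures planned group contact before the review. It is not an estimate of the risk of a breach. The issue is participant privacy, with no bearing on sample size, endpoints or analysis.

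**What to change.** In the section 8 Intervention Description, add an item (g) to the first individual session: the CHW goes over the ground rules and asks the participant not to discuss other members' personal information and not to share their names. Reword the sentence about the session after week 8 so that it is plainly a reminder of those rules. In section 13, Breach of Confidentiality Risk, state the same timing: asked before the first walk, repeated after week 8.

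The cost is one sentence of protocol text, with matching wording in section 13 and the manual, and a few minutes of a 30-minute session that already exists. No visit or staff time is added. If the manual or consent form already makes the request before the walks, only the protocol wording needs to change.

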**10) Data Management\***

As a pilot study, we will evaluate the feasibility of recruitment, assessment procedures, retention, acceptability, and implementation of HOLA in a sample of midlife and older Latinos LWH (**Aim 1**). Consistent with recommendations from biostatistical workgroups funded by NIH, this pilot study is not powered to test a hypothesis. This approach to analysis of feasibility data mirrors the structure of the first HOLA trial and other pilot trials conducted at the CNSA. Successful recruitment will be defined as meeting 100% of targeted sample (N = 30), with 20% or less of eligible subjects refusing to participate. Adequate retention will be defined as 85% or more of randomized subjects completing the post-intervention assessment. Acceptability is defined as 80% or more of sessions attended by subjects. To identify modifications needed in the design of a larger, confirmatory randomized controlled trial (**Aim 2**), we will use a project evaluation questionnaire developed by investigators at the CNSA and used in previous studies. The items are a mix of rating scales, yes/no questions, and open-ended questions that allow participants to give feedback in short

IRB Study Number: 20201202  
Version 4.02, Date: 11/10/2021

answer format with specific interest in understanding the participants' opinions regarding the specific components of the intervention. To explore changes in cognitive decline risk factors (waist circumference, dyslipidemia, hypertension, and glucose), psychosocial functioning (depression and anxiety severity, social support), and health-related quality of life (**Aim 3**), a one-way ANOVA will be used to illustrate the change in scores from baseline to post-intervention in all the outcome measures used.

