A repeated measures ANOVA, as we have proposed, is appropriate to explore the intervention effects on cardiometabolic risk factors, psychosocial functioning, and health-related quality of life given that this type of analysis is often used in studies that investigate either changes in mean scores over three or more time points. In the exploratory analyses, we will use age, SES, and years of education as covariates. In addition, a list of current medications will also be collected at baseline. Should the participants' medications be dose-adjusted, changed altogether, or if they are started on new medications such as statins, then we will adjust for them in them in the exploratory analysis as well. Covariates will be tested as moderators of treatment response.

Maintenance of Confidentiality:

Our staff is CITI certified and trained with maintenance of confidentiality. The information provided by study participants will be held as personal and confidential to the extent permitted by law. In addition to the safeguards included as part of the recruitment and screening process by assigning a patient a study ID to de-identify participants, all study participants will be given the contact information for the Principal Investigators to answer any questions that may arise. Participants will be informed that they may end their participation at any time without affecting access to any other services they are currently receiving. All study procedures will be conducted according to good clinical practice and all other relevant regulatory guidelines.

All electronic data will be stripped of identifiers and stored in password-protected files on servers at the Department of Psychiatry and Behavioral Sciences. These data are password secured for minimal access to authorized personnel associated with the study. For each data file, a code number will be assigned, and the master list, linking code numbers with names, will be stored separately. At the conclusion of the project, the record linking the assigned research number and participant identity will be destroyed. Data will be entered into password secured databases by staff authorized by the principal investigator to do this, and they will abide by confidentiality regulations of the HSRO. No subject will be identified by any published report.

IRB Study Number: 20201202  
Version 4.02, Date: 11/10/2021

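### HOLA is delivered in walking groups of 6, but the analysis of change has no group term; if change is correlated within groups, a within-person analysis will overstate precision.

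*Combined protocol and SAP*

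**What the plan says.** Section 8, under the description of HOLA, sets out a CHW-led group walk three times a week for 16 weeks, which is 48 sessions, and states: "Walks will be conducted with a group of 6 participants". Section 6 states that "30 older Latinos age 50+ will be enrolled". The number of groups is not given, but 30/6 = 5.

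The group is part of the treatment. When participants report on their planned pleasant events, "the CHW and the group provide positive reinforcement and feedback". More than one CHW is foreseen: "A fidelity measure has been developed to assess the consistency with which different CHWs deliver the HOLA intervention". How many CHWs there are, and which groups each leads, is not stated.

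Section 10 describes the analysis of change twice. First, "a one-way ANOVA will be used to illustrate the change in scores from baseline to post-intervention in all the outcome measures used". Then, "A repeated measures ANOVA, as we have proposed, is appropriate to explore the intervention effects". The listed covariates are age, SES, years of education and medication changes. Walking group and CHW appear nowhere as a factor or random effect, and no ICC, design effect or cluster-robust standard error is mentioned.

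**The concern.** People who share a group, a leader, 48 walks and mutual reinforcement may change together. Depression, anxiety and perceived social support are outcomes on which this is easy to imagine. If they do change together, 30 participants carry less information about mean change than 30 independent people, and an analysis without a group term reports more precision than it has.

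Section 3 says that the pilot is to give preliminary effects for a fully powered randomized trial. With no hypothesis test claimed, the estimates and their uncertainty are what the change analyses offer that trial. Group membership that is not recorded as the study runs may not be recoverable later.

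**Working it through.** **Inputs.** N = 30 (Section 6); group size m = 6 (Section 8); hence 5 groups. The 85% retention target (Endpoints) gives 0.85 × 30 = 25.5, so 26 completers. The documents give no ICC, SD of change or baseline/post-test correlation, so these are assumed over a range. The plan states no power, alpha or interval width, so it has no figure of its own to reproduce.

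**Within-person analysis of change.** Design effect DE = 1 + (m − 1) × ICC = 1 + 5 × ICC. Effective N = 30/DE. The true standard error is √DE times the one that assumes independence. Half-widths below are in units of the SD of change:
- Unadjusted: t(29)/√30 = 2.045/5.477 = 0.373.
- Group-level: t(4) × √(DE/30), with t(4) = 2.776.

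Coverage of the unadjusted nominal 95% interval comes from simulation (200,000 runs per ICC, 5 groups of 6).

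| Assumed ICC | DE | Effective N | SE ratio | Coverage, unadjusted | Half-width, group-level |
|---|---|---|---|---|---|
| 0 | 1.00 | 30.0 | 1.00 | 95.0% | 0.51 |
| 0.01 | 1.05 | 28.6 | 1.02 | 94.5% | 0.52 |
| 0.05 | 1.25 | 24.0 | 1.12 | 92.1% | 0.57 |
| 0.10 | 1.50 | 20.0 | 1.22 | 89.1% | 0.62 |
| 0.20 | 2.00 | 15.0 | 1.41 | 83.2% | 0.72 |

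The t interval on the 5 group means covers about 95% in every row, and also with 26 completers spread unequally over the groups. The half-widths in the table use the true SD. Averaged over samples with an estimated SD on 4 df (factor 0.940), they are 0.567 × 0.940 = 0.53 at ICC 0.05 and 0.621 × 0.940 = 0.58 at ICC 0.10. The unadjusted average is 0.37.

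**One-way ANOVA taken literally.** If baseline and post-test are treated as independent samples, the standard error is 1/√(1 − r) times the paired one, where r is the baseline/post-test correlation: 1.41 at r = 0.5 and 1.83 at r = 0.7. This error runs the other way. It is outweighed by clustering only when 1 + 5 × ICC exceeds 1/(1 − r), that is, when ICC exceeds (2 − 1)/5 = 0.20 at r = 0.5, or (3.33 − 1)/5 = 0.47 at r = 0.7.

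**What 5 groups say about the ICC.** In the same simulation with a true ICC of 0.05, the middle 95% of ANOVA estimates runs from −0.16 to 0.36, and 44% are negative.

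**The case against.** The case for leaving the plan alone has four parts.

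- **The loss may be negligible.** No ICC is given, and at 0.01 coverage is 94.5%. This stands: the statement is conditional on a positive ICC.
- **The direction is not settled.** A literal one-way ANOVA could give intervals that are too wide. This also stands, and it is why the two ANOVA statements must be reconciled first. Neither of them handles groups, so the omission remains.
- **No intervals are promised.** Section 10 says only that "a one-way ANOVA will be used to illustrate the change in scores from baseline to post-intervention". The figures therefore describe any interval or p-value later drawn from the ANOVA, not a number that the plan commits to. That sentence is also tied to Aim 3 and reaches cognition only through its closing reference to all outcome measures.
- **The stakes are limited.** The primary outcome is a set of feasibility thresholds, and the plan disclaims power to test hypotheses. This holds and keeps the point modest.

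A reader might also infer three stronger things that the documents do not support. The fidelity scale does not show that the sponsor expects CHWs to differ; with supervision and correction of drift, it is a control against that. The documents do not say that the later trial will use the same groups; its delivery format is not described. And adding a group term would not supply that trial with a design effect, because 5 groups estimate the ICC too poorly.

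**Conclusion.** The point holds in conditional form. Delivery is in groups and the planned analysis ignores this. If the ICC of change is positive and the analysis is within person, precision is overstated: the true standard error is 2%, 12%, 22% or 41% larger than the unadjusted one at assumed ICCs of 0.01, 0.05, 0.10 or 0.20. The calculation assumes 5 independent groups of 6, and coverage of the group-level interval was also checked with about 26 unequal completers.

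It would go too far to say that every interval for change is too narrow: the ICC is unknown, one of the two stated analyses could err in the opposite direction, and no interval is specified. The feasibility thresholds and the sample size are untouched. This is an inexpensive improvement to the exploratory analyses.

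**What to change.** 1. In Section 10, reconcile the one-way and repeated measures statements into one within-person analysis of change from baseline to 16 weeks.
2. Record walking group and CHW for each participant.
3. For each change outcome, report a t interval on the 5 group means (4 df) beside the unadjusted interval. If one CHW leads several groups, say so, since this interval treats the groups as independent.
4. Report the between-group variance or ICC only with its interval. If the later trial keeps group delivery, plan it over a range of ICCs.

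A random group intercept is an alternative but not an equivalent. In simulation the group variance was estimated at zero in 44% of runs at ICC 0.05 and 33% at ICC 0.10; there, if given about 29 df, the model returns essentially the unadjusted interval. The group-mean interval avoids this.

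The cost is two recorded variables, one extra line per outcome and a wider interval. At ICC 0.05 to 0.10 the average half-width rises from 0.37 to between 0.53 and 0.58 SD of change, about 1.4 to 1.6 times as wide (0.53/0.37 and 0.58/0.37). Enrolment, assessments and the intervention do not change.
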